13.2. Missing Data Imputation Rules

Partial missing dates will be imputed for start/stop dates of AE and prior/concomitant medications, as well as start date of each pericarditis episode according to the rules below.

Table 8: Imputation Rules for Partial Missing Dates

Category	Scenario	Rule for missing dates
General rule	All	If year is missing, do not impute, unless otherwise specified
AE and prior/concomitant medication start date	Day is missing and (month, year) same as the first dose date	The day will be imputed as the same day of the first dose day or stop date, whichever is earlier.
	Day is missing and (month, year) not the same as the first dose date	The day will be imputed as the first day of the month or stop date, whichever is earlier.
	Month and day missing, year the same as the first dose date	Date will be imputed with the first dose date or stop date, whichever is earlier.
	Month and day missing, year different from the first dose date	Impute with the first day of the year.
AE and prior/concomitant medication end date	Day is missing	Impute with min(last day of the month, data cutoff, end of study date)
	Day and month are missing	Impute with min(last day of the year, data cutoff, end of study date)
	Entirely missing	Impute with min(data cutoff, end of study date)
First pericarditis episode start date	Day missing	Use first day of the month
	Month missing	Use January 01
Second or later pericarditis episode start date	Day missing	Use max(first day of the month, stop day of previous episode +1)
	Month missing	January 01
Other	Non-specific	For missing data handling rules not covered in this table, they will be defined in the ADaM Define file.

13.3. EQ-5D-5L Scoring

The EQ-5D-5L consists of 2 pages – the EQ-5D-5L descriptive system and the EQ Visual Analogue scale (EQ VAS). The descriptive system comprises of 5 dimensions (mobility, self-care, usual activities, pain/discomfort, anxiety/depression). Each dimension now has 5 levels: no problems, slight problems, moderate problems, severe problems, and extreme problems. The respondent is asked to indicate his/her health state by ticking (or placing a cross) in the box against the most appropriate statement in each of the 5 dimensions. This decision results in a 1-digit number expressing the level selected for that dimension. The digits for 5 dimensions can be combined in a 5-digit number describing the respondent's health state. It should be noted that the numerals 1-5 have no arithmetic properties and should not be used as a cardinal score.

EQ-5D-5L health states, defined by the EQ-5D-5L descriptive system, may be converted into a single index value. The index values, presented in country specific value sets, are a major feature of the EQ-5D instrument, facilitating the calculation of quality-adjusted life years (QALYs) that are used to inform economic evaluations of health care interventions.

The EQ VAS records the respondent's self-rated health on a 20 cm vertical, visual analogue scale with endpoints labelled 'the best health you can imagine' and 'the worst health you can imagine'. This information can be used as a quantitative measure of health as judged by the individual respondents. The EQ VAS asks respondents to simply 'mark an X on the scale to indicate how your health is TODAY' and then to 'write the number you marked on the scale in the box below'.

The EQ-5D-5L Crosswalk Index Value Calculator can be found using the following link: <https://euroqol.org/eq-5d-instruments/eq-5d-5l-about/valuation-standard-value-sets/crosswalk-index-value-calculator/>

13.4. Calculation of 95% CI for Incidence Rate per 100 Subject-Years of Exposure/Observation

We first construct a formula to calculate the exact $100(1-\alpha)\%$ 2-sided CI for the number of events in a time interval. When this formula is applied to the number of events in a time interval of 100 subject-years in a study, we obtain the desired result to construct Fisher's exact 2-sided $100(1-\alpha)\%$ confidence interval for an incidence rate of interest per 100 subject-years. When $\alpha = 0.05$, it provides a 95% CI.

The number of events of interest in a time interval can be modelled using a Poisson distribution with parameter λ , where λ is the average number of events in this time interval. The probability of observing k events in this time interval is:

$$P(k \text{ events in interval}) = e^{-\lambda} \frac{\lambda^k}{k!}$$

If k events were observed in the interval, the lower bound l and upper bound u of the $100(1-\alpha)\%$ CI must satisfy the following conditions for Fisher's exact CI:

$$\text{Lower bound: } \sum_{x=0}^k \frac{e^{-l} l^x}{x!} = 1 - \alpha / 2$$

$$\text{Upper bound: } \sum_{x=0}^k \frac{e^{-u} u^x}{x!} = 1 - \alpha / 2$$

The parameter λ can be estimated with k . Using the relationship between the cumulative distribution functions of the Poisson and chi-squared distributions, the above lower and upper bounds can be expressed as follows:

$$\frac{1}{2} x^2 \left(\frac{\alpha}{2}; 2k \right) \leq \lambda \leq \frac{1}{2} x^2 \left(1 - \frac{\alpha}{2}; 2k + 2 \right), \quad (1)$$

where $x^2(a; v)$ is the chi-square quantile for lower tail probability with v degrees of freedom.

The inequalities in (1) are used in the SAS macro below to construct the confidence interval for the number of events. The lower bound, number of events, and upper bound are divided by the total treatment exposure expressed as subject-year to construct the incidence rate and its CI. Each number is then multiplied by 100 to obtain the incidence rate per 100 subject-years.

SAS Macro for the 95% CI of incidence rate per 100 subject-years

```
%macro nppy(x=5, n=100, alpha=0.05);
```

```
*** x=5 --# of events;
```

```
*** n = # of subject-years.;
```

```
*** alpha=2-sided type-I error rate, alpha=0.05 for 95% CI.;
```

```
data temp;
```

```
x=&x;
```

```
n=&n;
```

```
alpha=α
```

```
length CI_coverage $12.;
```

```
CI_coverage=compress(round(100*(1-&alpha), 0.1))||'%';
```

```
r=round((x/n)*100, 0.001);
```

```
if x=0 then Lower_bound=0;
```

```
else Lower_bound = round((quantile('CHISQ',&alpha/2,2*&x)/2/n)*100, 0.001);
```

```
Upper_bound = round((quantile('CHISQ',1-&alpha/2,2*(x+1))/2/n)*100, 0.001);
```

```
label x='# of events'
```

```
n='# subject years'
```

```
r='# of events per 100 subject-years'
```

```
alpha='2-sided alpha';
```

```
call symput('ci', compress(ci_coverage));
```

```
proc print data=temp label noobs;
```

```
title1 "&CI confidence interval for # of events per 100 subject-years";
```

```
title2 '--Exact method using the relationship between Poisson and Chi Square  
distributions';
```

```
run;
```

```
%mend;
```

```
*%nppy(x=14, n=400, alpha=0.05);
```

Signature Page for RIM-CLIN-000261 v1.0

Approval	 01-Apr-2020 21:06:50 GMT+0000
----------	--

Approval	 01-Apr-2020 21:07:38 GMT+0000
----------	--

Approval	 01-Apr-2020 22:29:41 GMT+0000
----------	--

Signature Page for RIM-CLIN-000261 v1.0

STATISTICAL ANALYSIS PLAN

PHASE 3, DOUBLE-BLIND, PLACEBO-CONTROLLED, RANDOMIZED WITHDRAWAL STUDY WITH OPENLABEL EXTENSION, TO ASSESS THE EFFICACY AND SAFETY OF RILONACEPT TREATMENT IN SUBJECTS WITH RECURRENT PERICARDITIS – Riloncept inHibition of interleukin-1 Alpha and beta for recurrent Pericarditis: a pivotal Symptomatology and Outcomes stuDY (RHAPSODY)

Sponsor:	Kiniksa Pharmaceuticals, Ltd. [REDACTED] [REDACTED] [REDACTED] [REDACTED]
Study Drug:	Riloncept (KPL-914)
Protocol Number:	KPL-914-C002
Date of Issue:	16 JUN 2020
Version:	2.0

CONFIDENTIALITY STATEMENT

The information in this document is the property of Kiniksa Pharmaceuticals, Ltd. and contains proprietary and confidential information to be held in strict confidence and not disclosed to any third party, without prior written consent of Kiniksa Pharmaceuticals, Ltd. Persons within your organization to whom any information herein is disclosed is on a need-to-know basis solely to carry out the purpose of this document, and be informed that such information is confidential and shall not be further disclosed by them without prior written consent from Kiniksa Pharmaceuticals, Ltd. Documentation, data, and all other information generated during the clinical study is proprietary and confidential information of Kiniksa Pharmaceuticals, Ltd. and shall not be disclosed to any third party, without prior written consent of Kiniksa Pharmaceuticals, Ltd.

History of Changes

This document is prepared based on the following protocol version:

Version Number	Version Date	Description

Table 1:	Censoring Rules for Time to Pericarditis Recurrence in the RW Period	20
Table 2:	The 8 Domains in SF-36v2.....	26
Table 3:	SF-36v2 Health Survey Items Scored for the SF-6D	27
Table 4:	Study Schedule of Activities – Screening and Run-In Period.....	39
Table 5:	Study Schedule of Activities – Randomized Withdrawal	43
Table 6:	Study Schedule of Activities – Long Term Extension	46
Table 7:	Study Schedule of Activities – Supplemental Visits	48
Table 8:	Imputation Rules for Partial Missing Dates.....	50

LIST OF ABBREVIATIONS

Abbreviation	Definition
ADA	anti-drug antibodies
AE	adverse event
ALT	alanine aminotransferase
ANCOVA	Analysis of covariance
AST	aspartate aminotransferase
CEC	Clinical Endpoint Committee
CMH	Cochran–Mantel–Haenszel
CRO	Contract Research Organization
CRP	C-reactive protein
CS	corticosteroids
DMC	Data Monitoring Committee
ECG	electrocardiogram
ECHO	echocardiography; echocardiogram
eCRF	electronic case report form
EDC	electronic data capture
EORW	End of Randomized Withdrawal (visit)

Abbreviation	Definition
EOT	End of Treatment (visit)
EQ-5D-5L	5-level EuroQoL-5D
ESR	erythrocyte sedimentation rate
FDA	US Food and Drug Administration
GI	gastrointestinal
HDL	High density lipoprotein
HIV	human immunodeficiency virus
ICF	informed consent form
ISI	Insomnia Severity Index
ISR	injection site reaction
ITT	intent to treat
IV	intravenous(ly)
IWRS	interactive web response system
KM	Kaplan-Meier
KPL-914	rilonacept
LDL	Low density lipoprotein
LTE	Long Term Extension Treatment Period
MedDRA	Medical Dictionary for Regulatory Activities
cMRI	cardiac magnetic resonance imaging
MRI	magnetic resonance imaging
NMSC	Non Melanoma Skin Cancer
NSAID	nonsteroidal anti-inflammatory drug
NRS	Numerical Rating Scale
ORT	Oral Rescue Therapy
PGA-PA	Physician Global Assessment of Pericarditis Activity

Abbreviation	Definition
PGIPS	Patient Global Impression of Pericarditis Severity
PK	pharmacokinetic(s)
POC	point of care
RE	Role participation with emotional health problems in SF-6D
RI	Run-In (period)
RP	Role participation with physical health problems in SF-6D
RW	Randomized Withdrawal (period)
SAE	serious adverse event
SAP	Statistical Analysis Plan
SAS	Statistical Analysis System
SC	subcutaneous(ly)
SF-36	36-Item Short Form Health Survey
SFU	safety follow up
SOC	standard of care
TEAE	Treatment emergent adverse event
ULN	upper limit of normal
WBC	white blood cell

1. STUDY OBJECTIVES

1.1. Study Objectives

1.1.1. Primary Objective

The primary objective of this study is to assess the efficacy of rilonacept treatment in subjects with recurrent pericarditis.

1.1.2. Secondary Objectives

The secondary objective of this study is to assess the safety of rilonacept treatment in subjects with recurrent pericarditis.

2. STUDY DESIGN

2.1. Design Overview

This study has the following periods:

- **Screening period**, during which assessment of disease characteristics, baseline therapy, and the pretreatment workup is completed (up to 4 weeks).
- **Single-blind Run-In (RI) period** (12 weeks), during which blinded rilonacept is administered subcutaneously (SC) once weekly in all subjects after the loading dose of double injections. The RI period includes the following:
 - 1-week Stabilization period, during which blinded rilonacept is administered in addition to standard of care (SOC) pericarditis therapy and the ongoing pericarditis episode is treated.
 - 9-week Weaning period, during which subjects are weaned off background SOC pericarditis therapy, as applicable, while treatment with blinded rilonacept continues.
 - 2-week Monotherapy period during which subjects who have successfully weaned off background SOC pericarditis therapy will continue to receive blinded rilonacept.

In the single blind RI period (subjects are blinded regarding the time of transition from the single- blind to the double- blind- period), adult subjects ≥ 18 years old will receive rilonacept as an initial loading dose of 320 mg (2 SC injections of 160 mg each) at the RI baseline visit (2×2 mL), followed by a 160 mg (2 ml) SC dose once weekly throughout the RI period. Pediatric subjects (≥ 12 and < 18 years old) will receive an initial loading dose of rilonacept 4.4 mg/kg (2 SC injections of 2.2 mg/kg each) at the RI baseline visit (maximum 2×2 mL), and then 2.2 mg/kg (maximum 2 mL) SC once weekly throughout RI period.

Subjects who achieve clinical response at RI Week 12 defined as stopping background pericarditis therapy no later than Week 10 and weekly average of daily pericarditis pain score ≤ 2.0 on the 11-point Numerical Rating Scale (NRS) within the 7 days prior to and including the day of randomization on RI Week 12/Randomization Withdrawal (RW) baseline and a C-reactive protein (CRP) level ≤ 0.5 mg/dL at the RI Week 12/RW baseline visit, will proceed into the double-blind placebo-controlled RW period.

Subjects who do not achieve clinical response at RI Week 12/RW baseline on rilonacept monotherapy will be discontinued from study drug, transitioned to SOC pericarditis therapy at the Investigator's discretion and followed through the end of the RW period.

Additionally, after the randomized withdrawal period has been closed when at least 22 confirmed recurrent pericarditis events have been accrued, subjects who have not yet completed the full 12 weeks of RI period at that time will be allowed to continue tapering of concomitant meds in the RI period; those subjects who achieved clinical response by Week 12 will be given the option to receive open-label rilonacept in the Long-term Extension Treatment period (LTE) without having to proceed through the RW period.

- **Double-blind placebo-controlled RW period** (pericarditis recurrence event-driven duration), during which subjects who were able to stop background SOC pericarditis therapy and who achieve clinical response at RI Week 12/RW baseline are randomized in a double-blind manner at a 1:1 ratio to the following:
 - Rilonacept 160 mg (2.2 mg/kg in pediatric subjects) SC injections once weekly
 - Matching placebo SC injections once weekly

Pericarditis Recurrence in the RW Period

Pericarditis recurrence is defined as the recurrence of typical pericarditis pain associated with supportive objective evidence of pericarditis. Upon pericarditis recurrence, subjects who report at least 1 day with pericarditis pain measurement ≥ 4 on the 11 point NRS and have 1 CRP value ≥ 1 mg/dL (either on the same day or separated by no more than 7 days) will receive bailout rilonacept (2 open-label injections of 160 mg rilonacept [or 4.4 mg/kg for pediatric subjects] followed by once weekly open-label rilonacept SC injections of 160 mg [or 2.2 mg/kg for pediatric subjects]) irrespective of randomized treatment assignment and as soon as at least 5 days have passed since the last study drug injection. Sequential oral rescue therapy (ORT), i.e., analgesics first, then NSAIDs, and then colchicine, can be added if needed at the discretion of the Investigator, as outlined in the protocol and Pharmacy Manual.

Subjects with pericarditis recurrence and who do not meet the protocol criteria for bailout rilonacept will continue blinded study drug until the protocol criteria for bailout rilonacept are met or through the end of the RW period. For those subjects, sequential ORT can be added to blinded study drug at the discretion of the Investigator, as outlined in the protocol and Pharmacy Manual.

All suspected pericarditis recurrence events in the RW period will be formally adjudicated by the Clinical Endpoint Committee (CEC), and only events that are confirmed by the CEC as pericarditis recurrences will be used in the Primary Endpoint analysis.

- **Long-term Extension Treatment period (LTE)** (variable, up to 24 months), during which all subjects in the RW period (including subjects transitioned to open-label rilonacept upon pericarditis recurrence) and subjects who are in the Run-In period after closure of the RW period, will have an option to receive up to 24 months of open-label rilonacept 160 mg (or 2.2 mg/kg for pediatric subjects) SC injections once weekly based on their clinical status and at the discretion of the Investigator, after signing LTE informed consent.

Subjects will be reviewed at 18 months after their most recent recurrence, (i.e., the qualifying episode for their original study enrollment prior to enrolling in the RI

period or a recurrence in RW which was treated with bailout rilonacept, whichever is the later). During this month's visit, the Investigator and subject will decide whether to continue treatment with open-label rilonacept, to continue in the study off-treatment for observation and rilonacept bailout upon subsequent recurrence, or discontinuation from the LTE. This review may be supplemented by:

- cMRI and/or echocardiogram and/or additional diagnostic testing as determined by the Investigator.
- subjects may be unblinded at that time (if available) at the request of the Investigator per procedures outlined in the Unblinding Plan to assist in clinical decision-making.

Safety data will be reviewed throughout the LTE by the Data Monitoring Committee.

2.2. Schedule of Assessments

The schedule of assessments is in Section 13.1.

2.3. Sample Size Calculation and Randomization

2.3.1. Sample Size Calculation

Sample size calculation is based on the primary endpoint, time to pericarditis recurrence defined as the time from randomization to the date of the first pericarditis recurrence for each subject. Time to pericarditis recurrence is assumed to follow an exponential distribution. An event of interest is defined as a subject's first adjudicated recurrence of pericarditis. The following assumptions are used in the sample size calculation using EAST 6.4.1:

- 1-sided significance level: 2.5%
- Power: 90%
- Median time to event (in weeks) in placebo: 8
- Hazard ratio (rilonacept/placebo): 0.244
- Percentage of subjects in the RI period that will not reach RW: 10%.

Given these assumptions, a total of 22 adjudicated pericarditis recurrence events is required to achieve the power. About 25 subjects per arm (a total of 50 subjects) or more will be randomized. Considering 10% of subjects in the RI period that will not reach the RW period, approximately 56 subjects will be enrolled in this study.

Subject enrollment and the pericarditis recurrence event accrual will be closely monitored during the study. The monitoring activities will be done in a blinded fashion during the RW period. If the number of subjects randomized is less than 50 and/or the time anticipated for the number of events required for the analysis of primary efficacy endpoint significantly exceeds the projected timeline, additional subjects may be enrolled and/or randomized at Kiniksa Pharmaceutical's discretion. However, at this time it is anticipated that no more than 100 subjects will be enrolled into this study.

2.3.2. Randomization

Subjects who achieve clinical response at RI Week 12 (Section 2.1) will proceed into the double-blind placebo controlled RW period. An interactive web response system (IWRS) will be used to administer the randomization schedule. CRO Biostatistics will generate the

randomization schedule using SAS® software Version 9.4 or later (SAS Institute Inc, Cary, North Carolina) for the IWRS, which will link sequential subject randomization numbers to treatment codes. The randomization schedule will be stratified by 2 factors:

- Oral CS use at baseline (RI baseline, i.e., beginning of RI period): yes or no
- Diagnosis of recurrent idiopathic pericarditis (RI baseline): yes or no

2.4. Timing of Analysis

The data cutoff for the primary analysis will be the end of RW period. When at least 22 adjudicated pericarditis recurrence events have occurred, end of RW period will be announced. The sites will have their subjects return to the site for the end-of-RW assessment (EORW). Data cutoff will occur after all subjects have completed this assessment. All data for this cutoff will be used in the primary analysis for efficacy and safety.

After the RW period, there will be a Long-term Extension Treatment period. An analysis will also be conducted after the end of the study. Since the data cutoff for the primary analysis will be done by the end of RW period, summary for LTE period will not be included in the primary analysis.

No interim analysis for claiming efficacy is planned. Interim safety review will be conducted by a Data Monitoring Committee (DMC). The analysis will be performed by a designated CRO. Details are in DMC charter and DMC Statistical Analysis Plan (SAP).

2.5. Responsibilities

The statistical analysis for the study will be performed by Kiniksa Biostatistics or its designated CROs.

3. GENERAL STATISTICAL CONSIDERATIONS

3.1. General Methods

Statistical analysis will be performed using SAS® software Version 9.4 or later. Continuous variables will be summarized using the mean, the standard deviation, median, minimum value, and maximum value. Time-to-event variables will be summarized using percent censored, event rate, and 25th, 50th, and 75th percentiles with 95% CI, if estimable. Categorical variables will be summarized using frequency counts and percentages. Data will be listed in data listings.

At RI, RW, and LTE periods, baseline will be the last value before the first dose of study drug within each individual period unless otherwise specified. For change-over-time endpoints in the RW period, by-visit analysis will be performed at each scheduled visit for at least 24 weeks.

When weekly average of NRS is used, it will be calculated based on every 7 days starting on the day after the first injection in each period. If there are missing values during the 7- day period, the average will be calculated based on the non-missing values. If 50% or more values (≥ 4 days) are missing, the average value will be set to missing.

By-visit analyses will be based on nominal visits and observed data, with unscheduled visits excluded.

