3.2 Safety Endpoints

Summaries of safety endpoints are conducted by study period (RI, RW, and LTE period) only.

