5.3.2. Clinical Laboratory Parameters

Hematology, chemistry, lipid panel, and urinalysis results will be summarized and listed. Pregnancy test will not be summarized but will be listed. Summaries will include descriptive statistics for actual values and change from baseline. Shift tables from baseline condition to the condition at each visit will also be provided. The shift table will include subjects without data so that all subjects in the safety population at the baseline of each period (RI, RW, and LTE) will be included.

A summary of hepatic function abnormalities will be provided for the following criteria:

- >2xULN
- >3xULN
- >5xULN
- The number of percentage of subject's meeting the criteria for Hy's Law defined as elevations in ALT and/or AST of $\geq 3xULN$ with accompanying elevations in total bilirubin of $\geq 2xULN$ will also be summarized.

The incidence rate per 100 subject-years and its 95% CI for the following lab abnormalities will be calculated:

- Incidence of ALT >5xULN,

- Incidence of AST >5x ULN,
- Incidence of total bilirubin >2xULN
- Incidence of absolute neutrophil count (ANC) <1.0 x 10³ uL.

Multiple lab abnormalities within a subject will be counted as multiple events within the follow-up period defined in Section 5.3.1 .

Incidence rate per 100 subject years in a cohort = $100 \times (\# \text{ of different lab abnormalities from all subjects within the follow-up period}) / (\text{Sum of follow-up duration in years from all subjects in the cohort})$.

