5.3.2.3. Non-fasting Lipid Panel

Subjects treated with riloncept may experience increases in their lipids, including total cholesterol, low-density lipoprotein (LDL), high-density lipoprotein HDL, and triglycerides.

Non fasting measurements of total cholesterol, triglycerides, HDL, and direct LDL will be performed by central study laboratory as described in the Schedule of Assessments in Section 13.1.

Investigators should monitor the lipid profiles in study subjects and consider ordering fasting lipid panel and/or lipid lowering therapies as needed based on cardiovascular risk factors and current guidelines.

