5.3.3. Vital Signs

Descriptive summaries of actual values and changes from baseline will be calculated for Temperature, Systolic Blood Pressure (SBP), Diastolic Blood Pressure (DBP), Pulse Rate

(PR), Respiratory Rate (RR), temperature, and weight (kg). A data listing of vital signs will also be provided.

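### After the addendum, no planned long-term-extension change or shift table compares laboratory, lipid or vital-sign values with pre-drug values, and on-drug and off-drug baselines are pooled

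*SAP*

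**What the plan says.** SAP v2.0, Section 3.1, sets the default for all three periods, to apply where no other rule is given: "At RI, RW, and LTE periods, baseline will be the last value before the first dose of study drug within each individual period". The safety sections specify nothing else. Section 5.3.2 states "Summaries will include descriptive statistics for actual values and change from baseline" and builds its shift tables so that "all subjects in the safety population at the baseline of each period (RI, RW, and LTE) will be included". Section 5.3.3 is worded the same way for vital signs: "Descriptive summaries of actual values and changes from baseline will be calculated for" the listed measures.

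The design fixes what those baselines are. In the RI period (Section 2.1) "blinded rilonacept is administered subcutaneously (SC) once weekly in all subjects after the loading dose of double injections", for 12 weeks. Footnotes to Tables 4 and 5 make the RI Week 12 visit the RW baseline and the end-of-RW (EORW) visit the LTE baseline.

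Section 5.3.2.3 says that treated subjects "may experience increases in their lipids, including total cholesterol" and other lipid fractions. Section 5.3 of v2.0 also listed a study-overall safety summary running from RI through LTE, without stating its baseline. Section 3.2 of the addendum now reads: "Summaries of safety endpoints are conducted by study period (RI, RW, and LTE period) only".

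**The concern.** The LTE is the plan's source of data on up to 24 months of open-label treatment. A reader of its change and shift tables will want to know how far values have moved since before the drug was started. These tables cannot answer that. A lipid rise that develops in the run-in and persists becomes part of the LTE baseline for anyone still on drug, and the change column then reads about zero.

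The pooled LTE column has a second problem. Placebo subjects who never took bailout start the LTE off drug, so their change includes re-exposure. Subjects already on drug contribute only further drift. The pooled mean depends on the mix of the two groups and estimates neither quantity.

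**Working it through.** **The plan's own figures.** The SAP gives no figure on this point and no laboratory or lipid values. The illustration in step 3 borrows its design figures, so those were checked first. Schoenfeld events = (1.960 + 1.282)² / [0.25 × (ln 0.244)²] = 21.12, rounded up to 22, as Section 2.3.1 states.

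**Step 1. Drug status at each baseline (Section 2.1; Tables 4 and 5).**

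| Baseline | Who | Status |
|---|---|---|
| RI | all | pre-drug |
| RW (= RI Week 12) | all randomized | after 12 weeks of rilonacept |
| LTE | rilonacept arm still treated; bailed-out subjects; direct from RI | on rilonacept |
| LTE | placebo without bailout | off rilonacept |

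**Step 2. What each table shows.** Assume a pre-drug value of 100 and an effect D reached by RI Week 12 and held on drug. Assume a fraction w of D is lost on placebo, with w from 0.5 to 1. D and w are assumptions. For D = 10:

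| Table | Period baseline | RI baseline |
|---|---|---|
| RI change | +10 | +10 |
| RW change, rilonacept | 0 | +10 |
| RW change, placebo | −5 to −10 | +5 to 0 |
| RW between-arm difference | +5 to +10 | +5 to +10 |
| LTE change, already on drug | 0 | +10 |
| LTE change, placebo without bailout | +5 to +10 | +10 |

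The RW between-arm difference is the same in both columns because both arms share the same expected RW baseline. The results scale in proportion for D = 5 or 20. The loss is confined to within-arm change in RW and to change in LTE.

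**Step 3. Size of the pooled LTE mixture.** Assume 25 subjects per arm, equal follow-up, exponential times, everyone entering the LTE from RW and the rilonacept arm still on drug. Let x be the cumulative placebo hazard. Solve 25(1 − e^−x) + 25(1 − e^−0.244x) = 22, which gives x = 1.057. That is 16.3 placebo and 5.7 rilonacept events.

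- All placebo events bailed out and back at plateau: on-drug share = (25 + 16.3)/50 = 0.83, off-drug share 0.17.
- No bailout: on-drug share = 25/50 = 0.50, off-drug share 0.50.

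Apparent pooled LTE change = off-drug share × w × D. With w = 1 this is 0.17D to 0.50D. With w = 0.5 it is 0.09D to 0.25D. The change from RI baseline would be D in every case. Direct entrants from RI would raise the on-drug share and lower the apparent change further.

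**Step 4. What covers the gap for lipids.** The numeric thresholds in Section 5.3.2 are for liver tests, bilirubin and absolute neutrophil count (ANC); none is for lipids. Table 5 schedules lipids in RW at Week 24 and EORW only, and the recurrence visit in Table 7 has no lipid panel. With the design placebo median of 8 weeks, 0.5³ = 12.5% of placebo subjects, about 3 of 25, would be recurrence-free at Week 24. In the equal-follow-up illustration the 22nd event falls near week 1.057 × 8/ln 2 = 12.2, leaving 25 − 16.3 = 8.7 placebo subjects recurrence-free at EORW. The lipid contrast with untreated placebo could therefore rest on few subjects.

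**The case against.** A reader might infer that drug-induced changes are hidden altogether, or that the plan gives false reassurance. The documents do not support that. The RI tables start from the pre-drug value, and Table 4 schedules chemistry, hematology and lipids at both RI baseline and RI Week 12, so an effect complete by Week 12 appears there in full. A further rise after Week 12 would show against the later baselines. Actual values are summarized as well as changes. The liver, bilirubin and ANC criteria are absolute and need no baseline. In a shift table a persisting abnormality appears as abnormal at both times; it does not disappear.

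Nor is the RW baseline a fault. The arms are compared concurrently, and a fall on placebo is how a withdrawal design reveals a drug effect. Making RI baseline the main RW reference would be a questionable trade. That visit falls in an active episode (CRP of at least 1.0 mg/dL and pain of at least 4 within the preceding 7 days, Table 4 footnote) and before background therapy is weaned. Change from it in white cell count or temperature mixes drug effect with episode resolution.

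The reach of Addendum 3.2 is also open to argument. Its introduction describes a supplement on the LTE, so it may not alter the study-overall summary in the primary analysis at RW cutoff. For the LTE, which is the point here, it does apply.

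All of this stands and narrows the point. It does not remove it. The RI tables cannot show whether a change persists over the extension. Actual-value means are not within-subject comparisons, and the LTE set is only those who entered the extension, so setting LTE means against RI means mixes drug effect with who continued.

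**Conclusion.** The point holds for the LTE. Under Section 3.1 and Addendum 3.2, no planned LTE change or shift table for laboratory values, lipids or vital signs uses a pre-drug reference, and subjects on and off drug at LTE baseline are pooled. A sustained effect established in the run-in would show as about 0 in continuing subjects. That result needs only the assumption that the effect is complete by LTE baseline and stays there.

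The pooled range of 0.17D to 0.50D is an illustration. It also assumes full washout on placebo, equal follow-up and universal LTE entry, none of which the SAP states. Its upper end assumes no bailout, although Section 2.1 has subjects who meet the criteria receive it, so the true figure would probably lie below 0.50D.

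The gap matters most for lipids, where the SAP expects a rise and has no absolute threshold. The consequence is confined to descriptive safety reporting. The primary analysis, alpha and sample size are unaffected. It should be corrected because the correction is cheap.

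**What to change.** Keep the period baselines in Section 3.1 as the main reference, including for the randomized RW comparison. Then, in Sections 5.3.2 and 5.3.3 and in the addendum:

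- add LTE change and shift from RI baseline (last value before the first rilonacept dose) for lipids, laboratory values and vital signs, optionally as a second column in RW;
- present LTE change from LTE baseline separately for subjects on and off rilonacept at that baseline;
- add a note that RI baseline falls in an active episode on background therapy, so white cell count, temperature and other inflammation-sensitive values also reflect episode resolution and weaning.

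The data are already scheduled: Table 4 has chemistry, hematology, lipids and an abbreviated physical examination with vital signs at RI baseline. The cost is a few more tables and care in reading the inflammation-sensitive measures.
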